5.1 Agent Administration

Treatment will be administered on an outpatient basis. Reported adverse events and potential risks are described in [Section 7](#). Appropriate dose modifications are described in [Section 6](#). No investigational or commercial agents or therapies other than those described below may be administered with the intent to treat the patient's malignancy.

5.1.1 CTEP IND Agent: MK-3475

Trial treatment should be administered on Day 1 of each cycle after all procedures/assessments have been completed as detailed on the Study Calendar ([Section 10](#)). Trial treatment may be administered up to 3 days before or after the scheduled Day 1 of each cycle due to administrative reasons.

MK-3475 treatment will be administered on an outpatient basis.

MK-3475 will be administered as a 30-minute IV infusion (treatment cycle intervals may be increased due to toxicity as described in Section 6.1). Sites should make every effort to target infusion timing to be as close to 30 minutes as possible. A window of -5

minutes and +10 minutes is permitted (i.e., infusion time is 30 minutes: –5 min/+10 min).

Study Treatment

Drug	Dose Potency	Dose Frequency	Route of Administration	Regimen/ Treatment Period
MK-3475	2 mg/kg	every 3 weeks	IV infusion	Day 1 of each cycle

Note: Calculate the required dose amount (2 mg/kg) based on subject's baseline weight. The dose amount should be recalculated if the subject's weight changes by more than 10% from the baseline weight measurement. If the patient's weight changes again by 10% or more (either increase or decrease) from the most recent weight used for dose calculation, recalculation of the dose is required.

Protocol [Section 8.1](#) provides specific instructions for MK-3475 dose preparation, and drug administration.

Treatment with MK-3475 study drug may continue until one of the following events occurs:

- Documented disease progression warranting alternative systemic therapy
- Intercurrent illness that prevents further administration of treatment
- Unacceptable adverse experiences (see [Section 6.1](#)).
- Need for >2 dose delays due to toxicity as per the dose modification guidelines described in Section 6
- Patient withdraws consent
- If in the opinion of the investigator and CITN Coordinating Center, a change or temporary or permanent discontinuation of therapy would be in the best interest of the patient.
- Pregnancy in patient
- Patient completes 24 months of treatment with MK-3475
- In patients with documented disease progression, treatment with MK-3475 can continue until one of the above occurs or until there is an increase in tumor burden of 25% or more following initial confirmation of progression.

Note: Patients will receive up to 24 months of trial treatment calculated from the date of first dose. Subjects who stop MK-3475 after 24 months may be eligible for up to 1 year of additional trial treatment if they progress after stopping trial treatment provided they meet the requirements detailed in [Section 5.10](#).

The first radiologic assessment of tumor response status will be performed at Week 13 (as consistent with standard of care). This assessment shall occur before drug administration scheduled for Week 13. However, if a patient is found to be progressing on MK-3475 at this initial scan, the patient can continue on MK-3475 if otherwise stable (see criteria below). A confirmatory scan will be performed at week 17, as immunomodulatory therapies may result in an early increase in lesion size due to influx

of immune cells. This immune activation and infiltration reflects the therapeutic mechanism and, therefore, an early increase in tumor size in this context may herald a therapeutic response rather than progression.

Thus, it is recommended that a patient with an unconfirmed early (<17 weeks) progression should continue therapy with MK-3475 waiting for confirmation of disease progression, but ONLY if the following criteria are met:

- Absence of clinical signs and symptoms (including worsening of laboratory values) indicating clinically significant disease progression
- ECOG performance status ≤ 1
- Absence of rapid disease progression or threat to vital organs or critical anatomical sites (e.g., spinal cord compression) requiring urgent alternative medical intervention

As depicted in the [Overall Trial Schema](#), an MK-3475-treated patient whose progression is confirmed at the 17-week scan will discontinue therapy. Alternatively, if patient is otherwise clinically stable per criteria above, they may be continued on MK-3475 treatment. The next scan will be performed at Week 22 and then every 9 or 12 weeks per the [Patient Visit Timeline](#). MK-3475 will be discontinued if the tumor burden increases by 25% or more following initial confirmation of progression.

In patients without progression and in patients with progression who continue treatment with MK-3475, disease radiologic monitoring should continue to be assessed at 9-week intervals through the first year of treatment and then at 12-week intervals throughout the duration of the study. [Section 5.4](#) describes criteria for discontinuing treatment.

After a patient is discontinued from study therapy, an end of therapy visit should be performed as soon as possible following the decision to stop study drug treatment or in conjunction with last treatment visit if discontinuation of therapy is anticipated. A mandatory safety follow-up visit should be performed approximately 30 days after the last infusion of study medication. All AEs occurring within 30 days after the last dose of trial treatment will be recorded.

All patients who discontinue treatment due to progression will be followed for at least 30 days after their last dose of study drug or until initiation of a new anticancer treatment, whichever occurs first. After the safety follow-up visit, patients will be followed for survival via phone contact every 12 weeks.

Patients who discontinue study therapy without documented disease progression will have a mandatory safety follow-up visit approximately 30 days after the last infusion of study drug, and should continue to be monitored for disease status by radiologic imaging according to the guidelines described in the [Visit Requirements](#) and [Study Calendar](#) for post-treatment follow-up. Imaging may be performed at the investigative site or locally; scans will be collected and RECIST 1.1 assessments performed. Collection of disease assessments will continue until progression, start of a new anticancer therapy, death or end of study, whichever occurs first. Thereafter, patients who progressed or started new treatment will be followed for survival via phone contact every 12 weeks \pm 1 week.

AE reporting will begin with administration of first dose of study medication. All AEs occurring within 30 days after the last dose of study treatment will be reported. Serious adverse events (SAE) related and unrelated to trial treatment will be collected for 90 days after the last dose of trial treatment or the start of new anticancer treatment, whichever comes first. Afterwards, only SAEs that are related to trial treatment will be reported. All SAE should be reported to the Sponsor via CTEP Adverse Event Reporting System (CTEP AERS).

Patients who are discontinued from the study due to an unacceptable drug-related AE will be followed for resolution of the AE to Grade 0–1 or stabilization, and monitored for disease status by radiologic imaging until progression or initiation of a new therapy for their cancer, whichever occurs first.

Patients in whom MK-3475 is stopped due to AE, can have the agent restarted (rechallenged) after resolution of the AE to Grade 1. If the same AE occurs at the same grade, MK-3475 will be discontinued.

VISIT REQUIREMENTS (also refer to [Study Calendars](#)):

Screening phase (pre-study; Day -28 to day 0):

- Obtain informed consent
- Record demographics
- Obtain medical history
- Tumor imaging
- Tumor biopsies/archival tissue collection*

*If sufficient archival tumor tissue (at least 0.5 × 0.5 × 0.5 cm) collected before MK-3475 therapy is not available, a baseline biopsy (core biopsy, punch biopsy or excisional biopsy) will be obtained before enrolling in the study assuming this can be carried out safely.

Screening phase (pre-study, Day -14 to day 0)

- Record concomitant medications
- Physical exam
- Vital signs
- Performance status
- 12-lead electrocardiogram (EKG)
- Pulmonary function testing (for patients with a history of pulmonary disease, prolonged smoking history, or symptoms of respiratory dysfunction).
- Laboratory tests:
 - Urine or serum B-HCG in women*
 - Complete blood count (CBC) with differential
 - Comprehensive serum chemistry panel
 - Urinalysis
 - T3, FT4, and TSH

*For women of reproductive potential, a urine pregnancy test should be performed within 72 hours before first dose of trial treatment. If urine pregnancy results cannot be confirmed as negative, a serum pregnancy test performed by the local study site laboratory will be required.

Treatment Cycles (to be repeated every 3 weeks)

Cycle 1

Day 1 \pm 3, prior to MK-3475 administration

- AE evaluation
- Physical examination
- Vital signs, height and weight (height required only for first treatment visit)
- Performance status
- Laboratory tests:
 - Kyn/Trp ratio
 - IFN- γ ELISpot
 - Immunophenotyping
 - T cell gene expression and phenotyping
 - MCPyV antibody levels
 - Serum, plasma, and PBMC storage

On Day 1 \pm 3, MK-3475 is administered after above procedures completed.

After MK-3475 infusion, a 12-lead EKG is performed within 30 minutes of end of infusion.

Subsequent Cycles without Scheduled Tumor Imaging (every 3 weeks)*

*See study [Patient Visit Timeline](#) and [Study Calendar](#)

Day 1 \pm 3, prior to MK-3475 administration:

- Concomitant medications
- Review of AEs
- Physical examination (limited)
- Vital signs and weight
- Performance status
- Laboratory tests:
 - CBC with differential
 - Comprehensive serum chemistry panel
 - Urinalysis*
 - T3, FT4, and TSH*
- Optional tumor biopsy/tissue collection if safe and feasible (core biopsy, punch biopsy or excisional biopsy) in patients who have not achieved CR (either responding, stable or progressing lesions).

*Urinalysis and thyroid function testing to be performed at Baseline, Cycle 6, and then every 6 cycles after baseline. After baseline, this will correlate with visits when scans and correlative blood draws are not scheduled.

On Day 1 \pm 3, MK-3475 is administered after above procedures completed.

Subsequent Cycles with Tumor Imaging Scheduled*

*See [Patient Visit Timeline](#) and Study [Calendar](#)

Day 1, within 7 days, before MK-3475 administration.

- Tumor imaging [Frequency of imaging is every 9 weeks \pm 3 days (every 3rd cycle) for first year of treatment, and then every 12 weeks \pm 7 days (every 4th cycle) during second year of treatment].

Day 1 \pm 3, prior to MK-3475 administration*:

*Blood will be drawn for correlative studies during Year 1 of treatment; during Year 2, correlative blood draws are required only around time of confirmation of progressive disease or at time of discontinuation of study drug. Safety labs (CBC and comprehensive serum chemistry) will occur with every cycle.

- Concomitant medications
- Review of AEs
- Physical examination
- Vital signs and weight
- Performance status
- 12-lead EKG*
- Laboratory tests:
 - CBC with differential
 - Comprehensive serum chemistry panel
 - Kyn/Trp ratio
 - IFN- γ ELISpot
 - Immunophenotyping
 - T cell gene expression and phenotyping
 - MCPyV antibody levels
 - Serum, plasma, and PBMC storage
- Optional tumor biopsy/tissue collection if safe and feasible (core biopsy, punch biopsy or excisional biopsy) in patients who have not achieved CR (either responding, stable or progressing lesions).

On Day 1 \pm 3, MK-3475 is administered after above procedures completed.

*In Cycle 8 (and Cycle 1), 12-lead EKG is performed within 30 minutes after end of MK-3475 infusion.

Confirmatory Tumor Imaging

When tumor imaging is performed to confirm progressive disease (PD; refer to [Patient Visit Timeline](#)), the following laboratory tests should be performed. If not possible to schedule a blood draw around the time of confirmatory scan, blood for these laboratory tests will be collected at the end-of-therapy visit.

- CBC with differential
- Comprehensive serum chemistry panel
- Kyn/Trp ratio
- IFN- γ ELISpot
- Immunophenotyping

- T cell gene expression and phenotyping
- MCPyV antibody levels
- Serum, plasma, and PBMC storage
- Optional tumor biopsy/tissue collection (core biopsy, punch biopsy or excisional biopsy) if PD is confirmed.

End of Therapy

- (The End of Therapy Visit is performed as soon as possible following the decision to stop study drug treatment or in conjunction with last treatment visit if discontinuation of therapy is anticipated).
- Concomitant medications
- Review of AEs
- Physical exam
- Vital signs and weight
- 12-lead EKG
- Performance status
- Laboratory tests:
 - Urine or serum HCG in women
 - CBC with differential
 - Comprehensive serum chemistry panel
- Laboratory tests (if not collected at time of determination of CR, PR, or disease progression):
 - Kyn/Trp ratio
 - INF- γ ELISpot
 - Immunophenotyping
 - T cell gene expression and phenotyping
 - MCPyV antibody levels
 - Serum, plasma, and PBMC storage
- Tumor imaging (not required if scan was performed within prior 4 weeks).
- Optional tumor biopsy/tissue collection if safe and feasible (core biopsy, punch biopsy or excisional biopsy), in patients who have not achieved CR (either responding, stable or progressing lesions) ([Section 2.5.1](#)).

Post-Treatment Follow-Up

Post-Treatment Safety Follow-Up (30 Days Post Treatment \pm 3 days). (This visit may be combined with End of Treatment Visit if decision to discontinue treatment is delayed).

- Concomitant medications
- Review of AEs
 - All AEs occurring within 30 days after the last dose of study treatment will be reported. Serious adverse events (SAE) related and unrelated to trial treatment will be collected for 90 days after the last dose of trial treatment or the start of new anticancer treatment, whichever comes first. Afterwards, only SAEs that are related to trial treatment will be reported.
- Physical exam
- Vital signs and weight
- Performance status
- Laboratory tests:
 - Complete blood count (CBC) with differential
 - Comprehensive serum chemistry panel
 - Urinalysis
 - T3, FT4, and TSH

Post-Treatment Disease Assessments

- Upon discontinuation of treatment in patients without documented progression, radiologic imaging for disease assessment will continue either at the investigative site or locally. Imaging will be collected and evaluated per RECIST 1.1.
- Year 1 Post-Treatment: Imaging will be performed Q 3 months (+/-14 days) or as clinically indicated for the first year post-completion of treatment.
- Years 2 and 3 Post-Treatment: Imaging will be performed Q 6 months (\pm 1 month) or as clinically indicated during years 2 and 3 post-treatment.
- If the study remains open, imaging will be performed annually or as clinically indicated once patient has completed 3 years of follow up for disease assessment.
- Collection of standard of care disease assessments will continue until progression, start of a new anticancer therapy, death or end of study, whichever occurs first.

Survival Follow-Up Phone Contacts (every 12 weeks \pm 1 week)

Begin survival follow-up phone contacts after discontinuing MK-3475 due to disease progression or start of a new anticancer therapy (initiate 12 weeks \pm 1 week following the Post-Treatment Safety Follow-Up Visit). Survival follow-up will continue until death or the end of the study, whichever occurs first.

5.1.2 ***Other Agent(s): N/A***

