6. DOSING DELAYS/DOSE MODIFICATIONS

6.1 MK-3475 Dose Modifications

6.1.1 General MK-3475 Dose Modifications

MK-3475 will be withheld for drug-related Grade 4 hematologic toxicities, non-hematological toxicity \geq Grade 3 including laboratory abnormalities, and severe or life-threatening AEs.

The table below includes general guidelines for toxicities that are not listed in the AE-specific table (see [section 6.1.2](#)).

General Dose Modification Guidelines for Drug-Related Adverse Events.

Toxicity	Grade	Hold Treatment (Y/N)	Timing for restarting treatment	Dose/Schedule for restarting treatment	Discontinue Subject
Hematological Toxicity	1, 2, 3	No	N/A	N/A	N/A
	4	Yes	Toxicity resolves to Grade 0-1 or baseline	May increase the dosing interval by 1 week	Toxicity does not resolve within 12 weeks of last infusion Permanent discontinuation should be considered for any severe or life-threatening event

Toxicity	Grade	Hold Treatment (Y/N)	Timing for restarting treatment	Dose/Schedule for restarting treatment	Discontinue Subject
Non-hematological toxicity Note: Exception to be treated similar to grade 1 toxicity 
 • Grade 2 alopecia • Grade 2 fatigue For additional information regarding Adverse Events with a potential Immune-Etiology reference Section 6.1.2.	1	No	N/A	N/A	N/A
	2	Consider withholding for persistent symptoms	Toxicity resolves to Grade 0-1 or baseline	Clinical AE resolves within 4 weeks: Same dose and schedule Clinical AE does not resolve within 4 weeks: May increase the dosing interval by 1 week for each occurrence	Toxicity does not resolve within 12 weeks of last infusion
	3	Yes	Toxicity resolves to Grade 0-1 or baseline	May increase the dosing interval by 1 week for each occurrence	Toxicity does not resolve within 12 weeks of last infusion
	4	Yes	N/A	N/A	Subject must be discontinued

In case toxicity does not resolve to Grade 0-1 within 12 weeks after last infusion, trial treatment should be discontinued. With Principal Investigator agreement, subjects with a laboratory adverse event still at Grade 2 after 12 weeks may continue treatment in the trial only if asymptomatic and controlled. Patients who experience a recurrence of the same severe or life-threatening event at the same grade or greater with re-challenge of MK-3475 should be discontinued from trial treatment.

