Grade 3-4	Discontinue MK-3475 when AST or ALT >5.0 times ULN and/or total bilirubin >3.0 times ULN.	
 Consider appropriate consultation and liver biopsy to establish etiology of hepatic injury, if necessary. Treat with high-dose IV glucocorticosteroids for 24-48 hours. When symptoms improve to grade 1 or less, a steroid taper with dexamethasone 4 mg every 4 hours or prednisone at 1-2 mg/kg should be started and continued over no less than 4 weeks. If serum transaminase levels do not decrease 48 hours after initiation of systemic steroids, oral mycophenolate mofetil 500 mg every 12 hours may be given. Infliximab is not recommended due to its potential for hepatotoxicity^b. Several courses of steroid tapering may be necessary as symptoms may worsen when the steroid dose is decreased 			

Event(s)	CTCAE v5.0 Grade	Management / Next Dose for MK-3475	Action / Supportive Care Guidelines	Symptoms ^a	Differential Diagnosis
Nausea	≤Grade 1	No change in dose	
 Nausea should be treated aggressively, and consideration should be given in subsequent cycles to the administration of prophylactic antiemetic therapy according to standard institutional practice. Patients should be strongly encouraged to maintain liberal oral fluid intake. 		
	Grade 2	Hold until ≤Grade 1. Resume at same dose level. May increase dosing interval by 1 week if it takes more than 4 weeks for toxicities to resolve.			
	Grade 3	Hold until <Grade 2. May increase dosing interval by 1 week for each occurrence. Discontinue if toxicities do not resolve within 12 weeks.			
	Grade 4	Off protocol therapy			
Neutropenia	≤Grade 1	No change in dose			
	Grade 2	No change in dose			
	Grade 3	No change in dose			
	Grade 4	Hold until resolves to ≤Grade 1. May increase the dosing interval by 1 week. Discontinue if toxicities do not resolve within 12 weeks.			

Event(s)	CTCAE v5.0 Grade	Management / Next Dose for MK-3475	Action / Supportive Care Guidelines	Symptoms ^a	Differential Diagnosis

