
Grades 3 or 4
 
Grade 3: Prolonged (i.e., not rapidly responsive to symptomatic medication and/or brief interruption of infusion); recurrence of symptoms following initial improvement; hospitalization indicated for other clinical sequelae (e.g., renal impairment, pulmonary infiltrates)
 
Grade 4: Life-threatening; pressor or ventilatory support indicated
	
Stop Infusion and Monitor Symptoms. Subject is permanently discontinued from further trial treatment administration.
 
Dexamethasone should be administered at a dose of at least 24 mg per day (8 mg every 8 hours PO or IV) for up to three days. The dexamethasone dose will then be reduced step-wise over up to four days.
 
Additional supportive care, as per institutional guidelines. Appropriate medical therapy may include but is not limited to:
 
 IV fluids Antihistamines NSAIDS Acetaminophen Narcotics Oxygen Pressors Corticosteroids Epinephrine 
Increase monitoring of vital signs as medically indicated until the subject is deemed medically stable in the opinion of the investigator. Hospitalization may be indicated.
	
No subsequent dosing

Appropriate resuscitation equipment should be available in the room and a physician readily available during the period of drug administration. For Further information, please refer to the Common Terminology Criteria for Adverse Events v5.0 (CTCAE) at http://ctep.cancer.gov
		

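### Sections 5.1.1 and 6 disagree on when a repeat toxicity ends treatment, and the rechallenge sentence in 5.1.1 has no exclusions and an undefined trigger

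*Combined protocol and SAP*

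**What the plan says.** **Section 5.1.1** has three relevant provisions.

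- Rechallenge: "Patients in whom MK-3475 is stopped due to AE, can have the agent restarted (rechallenged) after resolution of the AE to Grade 1".
- Recurrence, in the next sentence: "If the same AE occurs at the same grade, MK-3475 will be discontinued".
- Delays, in the list of events that end treatment: "Need for >2 dose delays due to toxicity as per the dose modification guidelines described in Section 6".

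**Section 6.1.1** has its own recurrence rule, for patients with a "recurrence of the same severe or life-threatening event at the same grade or greater with re-challenge of MK-3475 should be discontinued". Its general table discontinues after non-hematological Grade 4 toxicity and gives no restart option. For non-hematological Grade 3 it holds, then restarts with an interval that may be lengthened at each occurrence.

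**Section 6.1.2**, nausea and vomiting rows: Grade 2 is held until Grade 1 or less and resumed at the same dose level, with no limit on repeats. For Grade 3 the drug is held and the row adds "May increase dosing interval by 1 week for each occurrence". The Grade 4 skin row ends treatment permanently.

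**Section 6.1.3**, for Grade 3 or 4 infusion reactions: "Subject is permanently discontinued from further trial treatment administration".

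**Section 5.4** also requires discontinuation for a Grade 3 drug-related infusion reaction. Neither 5.4 nor 5.7 (criteria to resume) repeats the limit on the number of delays.

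**The concern.** A site that opens 5.1.1 and a site that opens the Section 6 tables can reach different decisions for the same repeat toxicity. The rechallenge sentence in 5.1.1, read alone, could also lead a site to re-dose a patient whom Section 6 bars from further drug, which is a safety matter.

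The stop decision also reaches the data:

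- It determines extent of exposure (13.11) and the reasons for discontinuation (13.5.3).
- It enters the PFS sensitivity analysis in 13.5.1.2. That analysis counts patients who discontinued without documented progression or death as progressed, at the later of discontinuation and start of new therapy.
- A patient without progression who stops during the first treatment year moves from scans every 9 weeks (±3 days) to scans every 3 months (±14 days). This affects how finely PFS and duration of response are dated.

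**Working it through.** No arithmetic applies. The check runs test patients through each section.

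| Test patient | Section 5.1.1 | Section 6 | Result |
|---|---|---|---|
| 1. Grade 2 vomiting is held, resolves, drug resumes, Grade 2 vomiting returns | Discontinue | Vomiting row: hold and resume. The 6.1.1 recurrence stop is not triggered, because the event is not severe or life-threatening | Conflict, if a hold counts as *stopped* |
| 2. Grade 3 nausea recurs after rechallenge | Discontinue | 6.1.1 text: discontinue, if Grade 3 counts as severe. Nausea row: hold, then the interval may be lengthened at each occurrence | Tension mainly inside Section 6 |
| 3. Non-hematological Grade 4, Grade 4 skin event or Grade 3-4 infusion reaction, later resolved to Grade 1 | Restart permitted, if *stopped* includes permanent stops | No further dosing | Conflict on that reading only |
| 4. Third toxicity delay, different AEs, each resolved within 12 weeks | Stop | No count of delays | Both can be followed; the cross-reference leads nowhere |
| 5. Second Grade 2 pneumonitis, or Grade 2 infusion reaction again despite adequate premedication | Discontinue | Discontinue | Agreement |

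Rows 1 and 3 depend on what *stopped* means in the rechallenge sentence:

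- If it means a temporary hold only, row 1 is a conflict and row 3 falls away.
- If it means permanent discontinuation only, row 3 remains and row 1 weakens, because the recurrence sentence then follows on from permanent stops.
- If it means both, both rows remain.

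The text does not settle this. The rechallenge paragraph appears to contrast *stopped* with *discontinued*, while the Section 5 introduction uses *stopped* for permanent cessation. No reading removes rows 1 and 3 together.

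In row 2, the same wording on each occurrence appears in the 6.1.1 general table for non-hematological Grade 3 events and in the vomiting row, so the tension is not confined to nausea. Section 6.1.1 does not say whether *severe* means Grade 3.

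**The case against.** The strongest case on the other side has five parts.

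- **5.1.1 is not self-contained.** It lists unacceptable adverse experiences with a pointer to 6.1 and refers to 5.4 for discontinuation criteria. Section 5.4 already stops Grade 3 drug-related infusion reactions. This stands, and it makes re-dosing after a barred event less likely. It does not supply the exclusion missing from the rechallenge sentence.
- **Permission is not obligation.** The sentence says patients "can have the agent restarted (rechallenged) after resolution of the AE to Grade 1", whereas the Section 6 bars are mandatory. Not restarting satisfies both. This stands: a reader might infer that the two give opposite instructions, and the text does not support that.
- **The delay limit is an added cap.** A limit in 5.1.1 can be followed alongside tables that set none, and its reference to Section 6 may only identify which delays count. This stands. A reader might infer a contradiction here too, but the defect is only that Section 6, the place cited, has no count and that 5.4 and 5.7 do not repeat it.
- **6.1.2 is guidance.** It describes its table as guidelines subject to clinical judgment. That softens row 1 but does not say whether judgment may override the discontinuation wording in 5.1.1. It does not reach the Grade 4 rule in 6.1.1 or the infusion-reaction rule in 6.1.3.
- **There is some ordering.** Section 6.1.1 confines its general tables to toxicities not listed in 6.1.2. That ranks tables within Section 6; it does not rank 5.1.1 against Section 6.

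**Conclusion.** The point holds in a limited form. The clear disagreement is over repeat Grade 2 nausea or vomiting after a hold, taking a hold as *stopped*. The recurrence rules in 5.1.1 and 6.1.1 also differ in scope: the first covers any grade but only the same grade, the second only severe or life-threatening events but at the same grade or greater. There is a further tension within Section 6 for repeat Grade 3 events if Grade 3 counts as severe, and an unrestricted rechallenge permission whose reach depends on an undefined word.

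It would be wrong to conclude that the sections disagree on repeat toxicity throughout. They agree for a second pneumonitis of Grade 2 or higher and for a Grade 2 infusion reaction on rechallenge, and several Grade 2 rows in Section 6 require no hold at all.

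No size in patients can be given, because the text supplies no frequency of repeat holds. The Study Summary describes all 50 patients as enrolled (26 + 24), so the exposure is confined to those still on treatment or retreated under 5.10. Patients who discontinue for toxicity stay evaluable for response (13.3.2), and the Simon figures (9 + 15 = 24 patients, rejection at 3 or more responses) are untouched. The correction should be made because it is cheap and bears on safety.

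**What to change.** Reconcile the following so that one consistent set of rules on recurrence, number of delays and rechallenge appears wherever these topics arise:

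- 5.1.1: the list of events that end treatment, and the rechallenge paragraph;
- 5.4 and 5.7;
- 6.1.1: the general table and the recurrence text;
- 6.1.2: the nausea, vomiting and skin rows;
- 6.1.3.

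Define *stopped* in the rechallenge sentence, and state which section governs if they differ. Which recurrence rule, delay limit and rechallenge conditions apply is for the sponsor's clinical team; this review takes no position on them.

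The cost is amendment wording and site re-training. No visits, patients or changes to the statistical design are needed.
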